## 10. TREATMENT PLAN

### 10.1. STUDY TREATMENTS

The treatment to be used in this study is outlined below in **Table 4**.

**Table 4. Study Treatment**

Drug	Dose/ Potency	Dose Frequency	Route of Administration	Regimen/ Treatment Period	Use
Pembrolizumab	200 mg	Every 3 weeks	IV Infusion	Day 1 of each 3 week cycle	Experimental
Topotecan	1.25 mg/m  Days 1 to 5	Every 3 weeks	IV Infusion	Days 1-5 of each 3 week cycle	Standard/ Control

The pembrolizumab (MK-3475) dosing interval may be increased due to toxicity.

Study treatment should begin on the day of randomization and no later than 48 hours from the date on which treatment is allocated/assigned (or 72 hours if randomization occurs on a Friday).

#### **Experimental Arm**

**Pembrolizumab:** 200 mg IV every 21-days until progression of disease or unacceptable toxicities.

#### **Control Arm**

**Topotecan** at 1.25mg/m^2 on days 1 to 5 every 21-days until progression of disease or unacceptable toxicities. Pegfilgrastim can be administered on day 6, 7 or 8 of every cycle as determined by the investigator.

Patients with progression of disease by RECIST 1.1 will be allowed cross over to receive **pembrolizumab** 200 mg IV every 21-days for up to 1 year until progression of disease or unacceptable toxicities.

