### 3.3. STUDY DESIGN AND INTERVENTION

#### 3.3.1. Study Design and Intervention

This is a multi-institutional, randomized, phase II study of pembrolizumab compared to topotecan, administered to patients with SCLC who have progressed or relapsed after first-line treatment with etoposide and platinum (cisplatin or carboplatin). This study will be conducted to determine if there is an improvement in progression free survival for SCLC patients treated with pembrolizumab compared to the standard therapy of topotecan. RECIST 1.1 will be used for this analysis.

[figure not shown]
Patients with sensitive or refractory disease will be eligible for the study; where sensitive disease will be defined as those patients who relapse >60 days after the completion of the first-line of chemotherapy. Patients with treated brain metastases will be eligible. Those patients with underlying or previous paraneoplastic syndromes are not eligible.

Ninety-three patients will be randomized in a 2:1 fashion to pembrolizumab or topotecan. Patients will be stratified based on disease type (sensitive vs.

refractory). Patients who progress in the topotecan arm will be allowed to cross-over to the pembrolizumab arm. Tumor samples will be required before initiating new therapy (preferably a new specimen) and a repeat biopsy will be performed, if clinically feasible, on-treatment (during weeks 4 to 6) for those in the pembrolizumab arm and at the time of disease progression for those in the topotecan arm. Scans will be reviewed by the investigator or designee.

Secondary endpoints will include safety, objective response rate by RECIST 1.1 and overall survival. Correlatives, including analyses of tissue and blood, will be assessed as well, as described below.

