#### 15.1. SCHEDULE OF EVALUATIONS

The initial tumor imaging will be performed within 14 days prior to the first dose of study treatment. Scans performed as part of routine clinical management are acceptable for use as the screening scan if they are of diagnostic quality and performed within 14 days prior to the first dose of study treatment. On-study imaging will be performed every 6 weeks ( $42 \pm 7$  days) after the first dose of study treatment or more frequently if clinically indicated. The timing for imaging studies should **follow calendar days** and should not be adjusted for delays in cycle starts or extension of topotecan or pembrolizumab (MK-3475) cycle frequencies. The same imaging technique should be used in a patient throughout the study.

After the first documentation of progression while receiving pembrolizumab (MK-3475) alone it is at the discretion of the investigator to keep a clinically stable patient on study treatment or to stop study treatment until repeat imaging performed 4-6 weeks later confirms progression.

Clinical stability in a patient whose disease displays radiographic progression is defined as:

- Absence of symptoms and signs indicating clinically significant progression of disease (including worsening laboratory values).
- NO decline in ECOG performance status.
- Absence of rapid progression of disease or progressive tumor at critical anatomical sites (e.g. cord compression) requiring urgent alternative medical intervention.

Patients that are deemed clinically unstable are not required to have repeat imaging for confirmation. Upon repeat imaging, if progression is confirmed, then the patient will be discontinued from study treatment. As the primary endpoint is PFS, the date of the first scan that documented progression should be used. If progression is not confirmed, then the patient should resume/continue study treatment and have the next scan according to the every 6-week ( $42 \pm 7$  days) schedule from the first dose of study treatment. When feasible, patients should not be discontinued until progression is confirmed.

For patients who discontinue study treatment for reasons other than disease progression, imaging should continue according to the same schedule (every 6 weeks/ 42 ± 7 days) until the patient experiences confirmed disease progression or starts a new antineoplastic therapy.

Study eligibility will be according to RECIST 1.1 criteria.

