### 19.1. SAMPLE SIZE JUSTIFICATION

According to the findings from the phase III study studying topotecan vs CAV in the second-line treatment of SCLC patients and the phase III study comparing oral and intravenous topotecan, we expect a median PFS of 12 weeks for the control arm (C) and 20 weeks (a 67% increase) for the experimental therapy (E) in the pooled patient population with relapsed sensitive or refractory SCLC. Under the assumption of exponential survival time, it corresponds to a hazard ratio  $\lambda_E/\lambda_C = 0.60$ . Assuming an accrual rate of 4 randomized patients per month, it will take approximately 23 months to enroll 93 randomized patients (62 arm E and 31 arm C). With additional follow-up of 26 weeks (approximately 6 months) after the enrollment of the last patient, or approximately 86 events (59 arm E, 27 arm C), the study has approximately 82% power to reject the null hypothesis  $\lambda_E/\lambda_C = 1$  and accept the alternative hypothesis  $\lambda_E/\lambda_C < 1$  when the true  $\lambda_E/\lambda_C = 0.60$  using a stratified log rank test at a 1-sided significance level of 0.10.

Per above, eligible patients will be randomized with 2:1 allocation to two arms (E and C). The patients on arm C are allowed to receive pembrolizumab after progression. The final analysis is expected to take place 6 months after the last enrolled patient has been treated.

In the primary analysis, a stratified log rank test with equal weights over time will be used to test the PFS difference between two arms. As late treatment effect is often observed for immunotherapy, a weighted log rank test with Fleming-Harrington weights also will be used as a supplementary analysis to maximize the test efficiency for late treatment effect. More details can be found in the Analytic Method section.

Objective response rate (ORR) is a secondary endpoint. The sample size of the study is not determined by having adequate power to test ORR. With 62/31 patients on arm E/C, the study has approximately 82% power to differentiate  $ORR < 12\%$  versus  $ORR > 32\%$  at one-sided significance level of 0.10

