## 20. STATISTICAL ANALYSIS PLAN

The primary analysis will include all randomized patients but exclude ineligible patients or patients who cancel this study before receiving any protocol treatment.

The primary efficacy endpoint is PFS, which is defined as the time from the date of randomization to the date of earliest radiographic disease progression or death. If the subject does not experience radiographic disease progression or death, then the data will be censored at the date of the last disease assessment. PFS will be analyzed by Kaplan Meier methodology and compared between arm E and arm C, using a log-rank test stratified by disease type (sensitive vs refractory). A two-sided, stratified log-rank test P value will be provided. Median PFS time will be calculated and 95% confidence interval for median PFS will be presented. Overall survival (OS) will be analyzed in a similar manner as PFS.

Late treatment effect is often expected for immunotherapy. For this reason, a weighted log rank test with Harrington-Fleming weights that optimize the expected late treatment effect will be conducted as a supplementary analysis for both PFS and OS. In particular, the following three parameter settings will be used: (1)  $\rho = 0$  and  $\gamma = 0.5$ ; (2)  $\rho = 0$  and  $\gamma = 1$ ; and (3)  $\rho = 0$  and  $\gamma = 2$  (39).

The proportion of subjects with objective response as assessed by the investigator using RECIST version 1.1 will be evaluated for randomized subjects. The objective response rate will be estimated and compared between arm E and arm C, using a Cochran-Mantel-Haenszel (CMH) test stratified by tumor volume. A two-sided, stratified CMH test P value will be provided. In addition, a 95% confidence interval will be constructed for the estimated proportions. Similar analysis will be conducted for disease control rate (DCR), which is defined as the proportion of patients achieving complete, partial and stable disease after the protocol treatment.

All subjects who receive at least one dose of the study drug will be included in safety analysis. Treatment-related toxicity will be summarized by grade, type and system organ

class. Comparisons of the percentages of subjects experiencing an adverse event between arm E and arm C will be performed using Fisher's exact test.

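### The open-label, locally read progression call is both the topotecan arm's route to pembrolizumab and the primary PFS event, and Section 20 has no analysis that would show earlier calling on topotecan

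*Combined protocol and SAP*

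**What the plan says.** Section 8.4 states that the sponsor, investigator and patient all know the treatment. On reading, Section 3.3.1 says: "Scans will be reviewed by the investigator or designee". Section 9.2 uses the local reading (investigator assessment with site radiology) for patient management and allows scans more often than every 6 weeks when clinically indicated.

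For the topotecan arm, Section 10.1 says: "Patients with progression of disease by RECIST 1.1 will be allowed cross over to receive" pembrolizumab. It names no confirmatory scan or sponsor check before the switch.

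Section 20 has PFS "defined as the time from the date of randomization to the date of earliest radiographic disease progression or death". The test is a log-rank test stratified by sensitive versus refractory disease. The only supplementary PFS analyses are Fleming-Harrington weighted log-rank tests.

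Section 15.1.3 has baseline and follow-up sums of target-lesion dimensions calculated and reported. Section 15.1.4 gives the numeric rule for progression (20% and 0.5 cm over the minimum sum) together with new-lesion and non-target criteria.

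**The concern.** The person who judges progression knows the arm, and on topotecan that judgement gives the patient access to the experimental drug. A borderline scan can then be called progression one visit sooner than the same scan would be on pembrolizumab. Control PFS becomes shorter and the error favours pembrolizumab.

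Section 20 would not reveal this. The weighted log-rank tests use the same called dates and inherit any distortion. Nothing compares the call with the recorded sums, separates progression found at unscheduled scans, or counts discordant calls by arm.

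The test is already run at a liberal level and only 31 patients are on topotecan, so a few early calls matter. A positive PFS result could not be defended from the planned outputs against an obvious criticism of an open-label crossover trial.

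**Working it through.** **Inputs from Section 19.1.** 62 patients on pembrolizumab and 31 on topotecan; 86 events (59 and 27); medians 20 and 12 weeks; hazard ratio 0.60 under exponential times; 4 patients per month; 26 weeks of follow-up after the last enrolment; the test is made "using a stratified log rank test at a 1-sided significance level of 0.10". Scans are 6-weekly (Section 9.2).

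**The plan's own figure.** Section 19.1 says "the study has approximately 82% power to reject the null hypothesis". Schoenfeld's formula is

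power = Φ( √(d·p·(1−p)) · |ln HR| − z₀.₉₀ ).

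- With d = 86 and p = 2/3: √(86 × 2/9) = 4.372; 4.372 × 0.511 = 2.233; 2.233 − 1.282 = 0.951; Φ = 82.9%.
- With p = 59/86: 82.0%.

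The stated power reproduces.

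**How sensitive the test is to a spurious effect.** Put a false hazard ratio h in place of 0.60, with the true ratio equal to 1. The chance of a positive result is Φ(4.372 · |ln h| − 1.282):

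| Spurious h | One-sided error |
|---|---|
| 1.00 | 10.0% |
| 0.95 | 14.5% |
| 0.90 | 20.6% |
| 0.85 | 28.4% |

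**Simulating early calls under no true effect.** Both arms have the same exponential median. Progression is detected at the next 6-weekly scan. Each topotecan progression is moved one scan earlier with probability q, never before the first scan. Pembrolizumab calls are left unbiased. The test is an unstratified log-rank test at one-sided 0.10, with 6,000 trials per cell (Monte Carlo standard error about 0.4 to 0.6 points). With medians of 20 and 12 weeks and no early calls, the model gives 83.2% power, in line with the formula.

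| q | Common median 12 weeks | Common median 20 weeks |
|---|---|---|
| 0 | 11.1% | 10.7% |
| 10% | 14.2% | 13.0% |
| 20% | 16.8% | 14.0% |
| 30% | 19.9% | 16.1% |

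Across repeated runs with different random draws, the ranges are about 11-14%, 14-17% and 16-20% for q of 10%, 20% and 30%. The excess of up to about one point at q = 0 is present without any bias and should not be attributed to it.

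Progressions detected at the first scan cannot move. The share still event-free at week 6 is 2^(−6/12) = 0.71 or 2^(−6/20) = 0.81, so q = 30% moves about 0.30 × 0.71 = 21% or 0.30 × 0.81 = 24% of topotecan patients.

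**Allowing for deaths.** PFS includes death from any cause (Section 19), and a death cannot be called early. The table above treats every event as a scan call, which puts it at the upper end. With q = 30% and 30% of events being deaths, the error is about 14-17%. In a separate run at q = 30%, death shares of 0%, 20% and 35% gave 18.0%, 16.2% and 14.8% (12-week median) and 16.1%, 14.8% and 13.7% (20-week median).

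**What is assumed.** The early-call rates and death shares are not in the documents. The model shifts scheduled scans only; it does not model unscheduled scans.

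**The case against.** **Existing safeguards.** Footnote 17 of the Schedule of Assessments requires repeat imaging after first progression in clinically stable patients and is not limited to one arm. Section 15.1 asks that, where feasible, patients not be discontinued until progression is confirmed. Imaging follows calendar days, the rule for target lesions is numeric, site radiology takes part in the reading, and Section 21.7 allows source-data checks. These are real but partial. The repeat scan applies only to clinically stable patients, is read by the same unblinded site, and is not tied to crossover in Section 10.1. The detailed confirmation text in Section 15.1 is written for progression on pembrolizumab, and PFS is dated at the first documenting scan. The endpoint review in Section 17.2.3 serves safety reporting. None of these is a PFS analysis.

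**The pembrolizumab side.** A reader might infer a mirror-image incentive to call progression late on pembrolizumab because the call would end the drug. The documents do not support giving this much weight. After first progression, Section 15.1 says "it is at the discretion of the investigator to keep a clinically stable patient on study treatment" pending a repeat scan, and Section 16.2.1 allows an exception even after confirmed progression. An investigator can record progression without stopping pembrolizumab, so the argument rests on the topotecan side.

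**The remedy.** A derived rule takes new-lesion and non-target judgements as recorded, so a clean comparison would not prove absence of bias. Patients who cross over before meeting the derived rule must be handled explicitly or the analysis could mislead. Both objections stand; the second is met in the fix.

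**Conclusion.** The gap holds on the documents: one unblinded local call opens crossover and sets the primary endpoint, and Section 20 cannot show whether it was made earlier on topotecan. The direction of any such bias is clear.

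Its size is illustrative. From about 11% with no early calls, the one-sided 0.10 error would be about 11-14%, 14-17% and 16-20% at 10%, 20% and 30% early topotecan calls with no deaths among the events, and about 14-17% at 30% early calls with 30% deaths.

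A reader might infer that the trial's true error is 16-20%, or that early calling is expected. The documents support neither: they give no miscall rate, and the upper figures assume that every event is a scan call. The conclusion is that the plan needs a way to detect the problem, while the primary analysis itself can stand.

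**What to change.** Add to Section 20:

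1. A PFS sensitivity analysis with progression derived by program from recorded sums (20% and 0.5 cm over the minimum), new lesions and non-target status. For topotecan patients who cross over before meeting the derived rule, show both treatments: censored at the last pre-crossover scan, and counted as an event at the next scheduled scan. The first risks informative censoring and the second imputes an event, so neither should be shown alone.
2. A sensitivity analysis moving progression found at unscheduled scans to the next scheduled scan, in both arms. The simulated figures do not bear on this item; its basis is that Section 9.2 allows extra scans.
3. A table by arm of called progressions that do not meet the derived rule, and of unscheduled scans. Include symptomatic deterioration, which Section 15.1.4 reports as progression without objective evidence while Section 20 counts radiographic progression only; the two sections must be reconciled.

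Add a data-entry query when a called progression does not meet the rule. The primary analysis, sample size and crossover are unchanged.

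Cost: SAP wording, two programmed analyses, one table and an edit check. Section 15.1.3 says the sums are calculated and reported, but the case report forms are not in the documents and the data-form instruction in Section 16.1.2 concerns progression on pembrolizumab, so capture of lesion data in both arms should be checked. The limit is that measurements and the new-lesion and non-target judgements still come from the unblinded site, so bias is exposed and limited, not removed.

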**1. SYNOPSIS****1.1. STUDY SUMMARY**

Abbreviated Title	Pembrolizumab vs Topotecan in the Second-line Treatment of Patients with Small Cell Lung Cancer
Study Phase	Randomized Phase II
Clinical Indication	Small cell lung cancer (SCLC) patients in need of second-line therapy after standard platinum/etoposide chemotherapy.
Study Type	Interventional
Type of Control	Active control without placebo
Route of Administration	Intravenous
Study Blinding	Unblinded open-label
Treatment Groups	Topotecan every 3 weeks until progression of disease; at which point, patients can cross over to the pembrolizumab arm.  Pembrolizumab 200mg every 3 weeks until progression of disease or up to 24 months, whichever occurs first.
Number of Study Patients	Approximately 98 patients will be enrolled at an anticipated 10 sites.
Estimated Duration of Study	Approximately 19 to 23 months to accrue and enroll the patients, with an additional 6 months of follow-up to observe events for the primary endpoint of progression free survival after the last patient is started on study; we have included an additional 6 months to allow patients responding on study drug to remain on protocol.
Subject Eligibility	Patients with sensitive or refractory disease will be eligible for the study; where sensitive disease will be defined as those patients with disease progression after treatment with standard first-line etoposide/platinum $\geq 60$ days from completing chemotherapy, and refractory disease will be defined as patients with disease progression $< 60$ days from completing chemotherapy. Patients with treated brain metastases will be eligible. Patients with underlying or previous paraneoplastic syndromes are not eligible.
Study Objectives	The primary endpoint is to determine if there is an improvement in progression free survival for SCLC patients treated with pembrolizumab compared to topotecan. RECIST 1.1 will be used for this analysis.  Secondary endpoints will include safety, objective response rate by RECIST 1.1, and overall survival. Exploratory endpoints based on correlative studies will be assessed.

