Study Design	This is a multi-institutional, randomized, open-label phase II study of pembrolizumab compared to topotecan, administered to patients with SCLC who have progressed or relapsed after first-line treatment with etoposide and platinum. Patients will be randomized in a 2:1 fashion to receive pembrolizumab or topotecan. Participants in the topotecan arm that progress will be allowed to cross-over to the pembrolizumab arm.
Study Treatment Plan	Pembrolizumab Arm: Pembrolizumab will be administered via IV infusion at 200 mg every 3 weeks, and treatment continued for up to 24 months, until documented disease progression, unacceptable side effects or intercurrent illness that prevents further administration of treatment, investigators' decision to

	
withdraw the subject, subject withdraws consent, pregnancy of the patient, noncompliance of the patient, or for administrative reasons.
 
Topotecan Arm: Topotecan will be administered via IV infusion at 1.25 mg/m^2 on days 1 to 5 of a 3-week cycle. Pegfilgrastim may be given on day 6, 7, or 8 to offset neutropenia. Patients who progress in the topotecan arm will be allowed to cross-over to the pembrolizumab arm.

Efficacy Assessments	
Patients will be evaluated every 6 weeks (42 ± 7 days) with radiographic imaging to assess response to treatment. Investigators will make all treatment-based decisions using RECIST 1.1.

Safety Assessments	
Patients will be evaluated clinically by physical exam and with routine blood work every 21 days. Adverse events will be monitored throughout the Study and graded in severity according to the guidelines outlined in the NCI Common Terminology Criteria for Adverse Events (CTCAE) version 4.

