**1.2. STUDY SCHEMA (FIGURE 1)**

\*:With allowance of 5% ineligible, cancelling and unevaluable, the study plans to register 98 patients, and randomize 93.

Patients who progress on the topotecan arm may cross-over to receive treatment with pembrolizumab.

Treatment is to continue for up to 24 months post-randomization or until disease progression on pembrolizumab or an unacceptable adverse event.

Patients will be followed until death.

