##### 16.1.2. Disease Progression

Remove from protocol therapy any patient with disease progression by irRC while receiving pembrolizumab (MK-3475) document details, including tumor measurements, on data forms. After disease progression, patients should be followed for survival per the study calendar (Section 9).

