#### 16.2. PATIENT WITHDRAWAL/DISCONTINUATION CRITERIA

##### 16.2.1. Patient Withdrawal

In the absence of serious toxicity or complications, all patients will continue treatment until evidence of disease progression, or for up to 24 months, whichever is first.

Patients may withdraw consent at any time for any reason or be dropped from the study at the discretion of the investigator should any untoward effect occur. In addition, a patient may be withdrawn by the investigator or the Sponsor if enrollment into the study is inappropriate, the study plan is violated, or for administrative and/or other safety reasons. If, at any time the constraints of this protocol are detrimental to the patient's health and/or the

patient no longer wishes to continue protocol therapy, protocol therapy shall be discontinued.

A patient must be discontinued from the study for any of the following reasons:

- The patient or legal representative (such as a parent or legal guardian) withdraws consent.
- Confirmed radiographic disease progression while receiving pembrolizumab as per RECIST 1.1.  
*Note:* A patient may be granted an exception to continue on treatment with confirmed radiographic progression if clinically stable or clinically improved, per the investigator's discretion, given the potential of tumor flare.
- Unacceptable adverse experiences
- Intercurrent illness that prevents further administration of treatment
- Investigator's decision to withdraw the patient
- The patient has a confirmed positive serum pregnancy test
- Noncompliance with study treatment or procedure requirements
- The patient is lost to follow-up
- Administrative reasons

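### The protocol gives conflicting stopping rules for pembrolizumab: three different limits after crossover, a 24-month cap missing from the treatment plan for the randomised arm, and two progression criteria.

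*Combined protocol and SAP*

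**What the plan says.** **Pembrolizumab after crossover**
- Section 10.1, Control Arm: "200 mg IV every 21-days for up to 1 year until progression of disease or unacceptable toxicities".
- Section 1.2, Study Schema: "Treatment is to continue for up to 24 months post-randomization or until disease progression on pembrolizumab or an unacceptable adverse event". The clock starts at randomisation, so time on topotecan counts.
- Section 16.2.1: "all patients will continue treatment until evidence of disease progression, or for up to 24 months, whichever is first". No start date is given and no arm is excepted.
- Section 1.1 lets topotecan patients join the pembrolizumab arm and gives no separate crossover limit.

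**Randomised pembrolizumab**
- Section 1.1, Treatment Groups: "Pembrolizumab 200mg every 3 weeks until progression of disease or up to 24 months, whichever occurs first". The treatment plan row of the synopsis, the schema and 16.2.1 also give 24 months.
- Section 10.1, Experimental Arm: "200 mg IV every 21-days until progression of disease or unacceptable toxicities", with no time limit. Section 3.3.2 likewise lists reasons to stop without one.

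**Progression criterion**
- Section 16.1.2: "Remove from protocol therapy any patient with disease progression by irRC while receiving pembrolizumab". The body text does not define irRC; a guideline on immune-related response criteria appears only in the reference list (item 57).
- Section 1.1, repeated in 3.3.2: "Investigators will make all treatment-based decisions using RECIST 1.1". Section 16.2.1 uses confirmed progression by RECIST 1.1.

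**Study length**
- Section 1.1 estimates 19 to 23 months of accrual and 6 months of follow-up for PFS events, then adds: "we have included an additional 6 months to allow patients responding on study drug to remain on protocol".

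**The concern.** A site that follows one of these sections departs from another. The patients concerned are those still benefiting at one year or later, whose durable responses are part of the rationale for the trial. If stopping depends on which section a site reads, exposure to the same drug will vary for reasons unrelated to the patient or the randomised arm. That variation enters safety exposure, drug supply and overall survival, and OS and safety are secondary objectives (section 6.2). Section 21.9 says that the sponsor grants no deviation waivers, so sites have no informal way round the conflict. The estimated study duration adds a further doubt: it does not leave room for a 24-month course for patients who enter late.

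**Working it through.** **Inputs.** Section 19.1: 93 randomised (62 pembrolizumab, 31 topotecan), 4 per month, about 23 months of accrual, median PFS 12 weeks (topotecan) and 20 weeks (pembrolizumab), exponential, 86 events (59 and 27), hazard ratio 0.60, one-sided 0.10, 82% power. Section 1.1: accrual 19 to 23 months, then 6 + 6 months. Section 10.1: treatment starts within 48 to 72 hours of randomisation.

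**1. The plan's own figures reproduce.** Accrual: 93/4 = 23.25 months, against 23 stated. Power: Φ(√(86 × 2/3 × 1/3) × |ln 0.60| − 1.2816) = 0.829. With the stated 59/27 event split it is 0.820, against 82% stated. Neither calculation uses a treatment cap.

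**2. Crossover at week 12** (24 months taken as 104 weeks)

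| Source | Weeks of pembrolizumab | Three-weekly doses |
|---|---|---|
| 10.1: 1 year | 52 | about 18 |
| Schema: 24 months from randomisation | 104 − 12 = 92 | about 31 |
| 16.2.1: 24 months, read as time on pembrolizumab | 104 | about 35 |

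The longer limits exceed the shortest by 40 and 52 weeks, or about 13 and 17 cycles. The first two rows agree only if crossover falls exactly at month 12.

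**3. Randomised pembrolizumab.** Treatment starts within 48 to 72 hours of randomisation, so 24 months and 24 months from randomisation differ by only 2 to 3 days. The conflict in this arm is a 24-month cap against no stated cap.

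**4. Patients still progression-free when the limits apply.** S(t) = 2^(−t/20), t in weeks.
- 52 weeks: 2^(−2.6) = 0.165; × 62 = 10.2.
- 104 weeks: 2^(−5.2) = 0.027; × 62 = 1.7.
- Crossover: the documents give no number crossing over. Assuming 10 to 31, and assuming that the 20-week median also holds after crossover, 10 × 0.165 = 1.6 to 31 × 0.165 = 5.1, or about 2 to 5 patients progression-free at one year on pembrolizumab.

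**5. Study length**
- Stated: 19 + 6 + 6 = 31 to 23 + 6 + 6 = 35 months, ending 12 months after the last patient starts.
- Needed for a 24-month course in the last patient: 19 + 24 = 43 to 23 + 24 = 47 months, 12 months more in both cases.
- Patients enrolled in the first 31 − 24 = 7 to 35 − 24 = 11 months can complete 24 months; those enrolled in the last 12 months cannot.
- Late-enrolled pembrolizumab patients, uniform accrual: 62 × 12/23 = 32 to 62 × 12/19 = 39.
- Progression-free 12 months after their own randomisation, the shortest time any of them has before the stated end: 32.3 × 0.165 = 5.3 to 39.2 × 0.165 = 6.5, about 5 to 6 patients.
- Their time to the stated end in fact runs from 52 to 104 weeks. The mean of S(t) over that range is (0.165 − 0.027)/(52 × ln 2/20) = 0.076. That gives 32.3 × 0.076 = 2.5 to 39.2 × 0.076 = 3.0, so about 2 to 3 of them would still be progression-free on the closing date itself.

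**The case against.** **A separate crossover limit may be deliberate.** Section 10.1 is the specific text, and the schema and 16.2.1 could be read as general ceilings. One year after crossover stays inside the schema's ceiling for anyone crossing by month 12, and on a 12-week median 1 − 2^(−52/12) = 95% have had a PFS event by then. This is a fair reading, but nothing says that 10.1 prevails. The schema expressly covers treatment until progression on pembrolizumab, and 16.2.1 speaks of all patients.

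**No cap in 10.1 and 3.3.2 is silence, not a contrary rule.** This is partly right: for the randomised arm it is an omission. However, the synopsis refers readers to the full protocol text for the treatment plan, and the cap is missing there.

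**The study duration is an estimate.** This stands. It is labelled approximate, and no section makes it a reason to stop treatment. A reader might infer that the stated length is incompatible with any 24-month course. It is not, because early enrollees can complete one. A reader might also count everyone randomised in the last year, about 12 × 4 = 48 of 93, as deprived of a full course. That count includes topotecan patients and the many who would already have progressed.

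**ORR by line of therapy.** A reader might infer that a promised second- versus third-line comparison is compromised. Section 5.1.2 promises only to determine ORR in each setting. With six-weekly scans and a 20-week median, a limit acting after one year should hardly alter it.

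**The progression criterion is a separate matter from duration.** That is true, but it also decides when pembrolizumab stops, and the same amendment can settle it.

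**Conclusion.** The conflict is real and is in the current text. After crossover, three sections allow about 52, 92 or 104 weeks of pembrolizumab to a patient who crosses at week 12. In the randomised arm, a 24-month cap appears in some sections and is absent from 3.3.2 and 10.1. Progression is judged by irRC in one section and by RECIST 1.1 in the others.

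The number of patients affected is small: about 10 of 62 at 52 weeks and 2 of 62 at 104 weeks in the pembrolizumab arm, and about 2 to 5 crossover patients. These counts rest on the plan's exponential 20-week median, on its holding after crossover, and on an assumed 10 to 31 crossovers. A longer tail than exponential would raise them.

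A reader might infer that the primary result is at risk. The documents do not support that: crossover follows the PFS event, progression is dated from the first scan showing it (section 15.1), and neither sample size nor power uses a treatment cap. The point concerns treatment exposure, safety exposure, drug supply and OS. It should be corrected, but it does not undermine the design.

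**What to change.** Reconcile sections 1.1 (treatment groups, treatment plan, efficacy assessments and estimated duration), 1.2, 3.3.2, 10.1 (both arms), 16.1.2 and 16.2.1:
- one duration limit for randomised pembrolizumab and the date it is counted from;
- one duration limit for pembrolizumab after crossover and the date it is counted from (randomisation or first pembrolizumab dose);
- one progression criterion for ending pembrolizumab, used throughout, and defined in the body text if it is not RECIST 1.1;
- an estimated study duration that matches those limits, or a sentence saying what happens to patients still on treatment when it ends.

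Which limits and which criterion apply is for the sponsor to decide. The cost is one wording amendment and possibly a longer stated study duration. Sample size and the primary analysis do not change.
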